5.1.7. Analysis of Safety Data

The analysis of safety and tolerability will be performed on the SAF-LTS, as defined in Section 3.2.

The safety analysis will be based on the reported AEs and other safety information (clinical laboratory evaluations, vital signs, 12-lead ECG, Physical Examination, etc.).

Treatment-Emergent Potential Clinically Significant Values (PCSV) in laboratory variables, vital signs and ECG are defined in [Appendix 11.2](#).

Period of observation: The observation period will be divided into three segments: pre-treatment, on-treatment and post-treatment.

- The pre-treatment period is defined as the time between when the patients give informed consent and the start of study drug.
- The LTS on-treatment period is defined as the time from first dose of study drug up to 28 days after the last dose of study drug. The LTS post-treatment period is defined as the time starting 29 days after last dose of study drug (after the on-treatment period) to up to 24 weeks post the last dose of study drug (up to week 72).

Day 1 is the first day of study drug, Day -1 is the day before Day 1, and there is no Day 0.

The time interval to detect any on-treatment event or abnormality is between the first dose of double-blind study drug injection and the end of treatment plus 28 days. Data collected outside this interval will be excluded from the estimation of descriptive statistics and identification of abnormalities for laboratory evaluations, ECGs and vital signs. All post-baseline data during the interval will be using in the PCSV analysis including scheduled and unscheduled assessments.

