Safety assessments will be performed at each study visit during treatment period 1, as outlined in [Table 1](#). Potential events of adjudicated arthropathy will be monitored via clinical signs and symptoms of worsening joint pain during the study (eg, using the joint pain questionnaire and imaging). Potential events of sympathetic nervous system dysfunction will be monitored throughout the study through physical examination, AE reporting, assessment of orthostatic hypotension and via the Survey of Autonomic Symptoms.

Efficacy assessments will be performed for patients participating in the sub-study as outlined in [Table 3](#). Sub-study patients should discontinue use of paracetamol/acetaminophen 24 hours prior to the start of study visits during treatment period 1 in order to minimize the confounding effects of the rescue medication on efficacy measurements.

- **Treatment Period 2 (starts with study drug administration at week 16 and continues through week 52):** Treatment period 2 begins at the week 16 visit and continues through the week 52 visit. Patients will continue to receive fasinumab 1 mg Q8W, 1 mg Q4W or placebo Q4W during this period. At the week 24 visit, X-rays of the hips, knees, and shoulders will be obtained. The last dose of study drug will be administered at week 48.

During treatment period 2, patients may use non-NSAID standard-of-care pain treatment as rescue treatment and limited use of oral NSAIDs for non-OA related pain or fever.

Non-steroidal anti-inflammatory drugs will be study-provided as tablets or capsules, and may be used for up to 10 days in an 8-week period, 30 days in a 6-month period, and 60 days in a 1-year period. Use of oral NSAIDs in excess of these amounts is prohibited. The daily dose should not exceed the recommended maximum daily dose per the product labeling. Topical NSAIDs are prohibited during treatment period 2. Patients may be withdrawn from the study after appropriate counseling if continued noncompliance with protocol-defined maximum NSAID use occurs.

Patients will continue to be supplied with paracetamol/acetaminophen during treatment period 2.

The use of paracetamol/acetaminophen and/or NSAIDs should be recorded daily by the patient in the patient's diary. All other pain medications will be obtained and used per local standard-of-care; their use will be reported as concomitant medication during regular study visits.

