### 9.5.3. Safety Analysis

The incidence rate is defined as the number of events divided by the duration of the overall observation period. The incidence rate will be summarized by treatment group along with 2-sided 95% confidence interval. The incidence rate differences and ratios between each fasinumab dose group and placebo will be computed and presented along with 2-sided 95% confidence intervals.

Change from baseline in joint space width of the index knee or hip will be summarized by treatment group. Time to event endpoints, such as time to JR decision, will be analyzed using the Kaplan-Meier approach.

For safety variables, the following observation periods are defined:

- The pretreatment period is defined as the time from signing the ICF to before the first dose of study drug
- The on-treatment period is defined as the day of the first dose of study drug to 4 weeks after the day of the last dose of SC study drug.
- The follow-up period is defined as from the end of the on-treatment period up to 24 weeks post the last dose of study drug (week 72).

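### The on-treatment cut-off in SAP 5.1.7 falls exactly on the week 52 target day, so laboratory, ECG and vital-sign values from an in-window but slightly late week 52 visit can drop out of the on-treatment summaries

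*SAP*

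**What the plan says.** SAP 5.1.7 sets the on-treatment period for the long-term safety study as "the time from first dose of study drug up to 28 days after the last dose of study drug". The post-treatment period is "the time starting 29 days after last dose of study drug (after the on-treatment period)" and runs "to up to 24 weeks post the last dose of study drug (up to week 72)". Protocol 9.5.3 has the same on-treatment definition in weeks: "the day of the first dose of study drug to 4 weeks after the day of the last dose of SC study drug". Neither text adds a visit-window allowance.

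The same SAP section then sets the interval for detecting on-treatment events, and here the upper limit is worded differently: "the end of treatment plus 28 days. Data collected outside this interval will be excluded from the estimation of descriptive statistics". The sentence goes on to abnormality identification and is limited to laboratory evaluations, ECGs and vital signs.

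Elsewhere the documents treat week 52 as part of treatment:

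- Protocol 3.1: "Treatment period 2 begins at the week 16 visit and continues through the week 52 visit", and "The last dose of study drug will be administered at week 48".
- SAP 4.5.1: the primary safety endpoint includes laboratory changes from baseline to week 52, spanning both treatment periods, as well as to week 72.
- SAP 6.4: by-visit summaries use the nominal visit. Assessments without one are mapped by study day, with days 352–393 assigned to week 52.

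**The concern.** A 28-day tail after a four-weekly dose is a normal convention. The difficulty is that here it ends on the very day the end-of-treatment visit is due. Whether the last planned treatment-period assessment counts as on-treatment then depends on appointment timing: a visit one day later than the last dose, each measured against its own target, is out.

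Week 52 carries much of the on-treatment information. By Protocol Tables 1 and 2 it is one of two scheduled post-baseline ECGs in the treatment period (weeks 28, 52), one of three hematology draws (16, 32, 52) and one of five chemistry draws (4, 8, 16, 32, 52). For ECG and vital signs the SAP also specifies post-treatment and overall PCSV summaries (5.1.8.4, 5.1.8.5), so a displaced value still appears somewhere. The laboratory section (5.1.8.3) specifies neither. A laboratory PCSV from a late week 52 draw would appear only in the listings.

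Patients who stop early meet the same edge. Their end-of-treatment assessments take place at the next scheduled visit (Protocol 6.2.7), nominally 28 days after an on-schedule dose.

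**Working it through.** **Inputs.** Last dose at week 48 (Protocol 3.1), target day 337; week 52 target day 365 (both SAP 6.4). Dosing window ±7 days (Protocol 5.1). Week 52/end-of-treatment visit window ±7 days (Protocol Table 2). Visits are scheduled from day 1, not from the previous dose (Protocol 6.2.4). The distribution of actual dates is not given and has to be assumed.

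**1. Where the cut falls.** Week 48 = 7×48 + 1 = 337. Week 52 = 7×52 + 1 = 365, which reproduces the SAP's target day. Period close = 337 + 28 = 365, the same day.

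**2. When a visit is outside.** Let D and V be the dose and visit deviations from target, each between −7 and +7 days. The gap is 28 + V − D, so the visit is outside when V > D. The largest in-window gap is 28 + 7 + 7 = 42 days.

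**3. Share outside under uniform timing.**
- Dose on target: days 366–372 are outside, 7 of 15 window days = 46.7%.
- D and V independent and uniform: P(V > D) = (1 − 1/15)/2 = 14/30 = 46.7%.

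**4. Sensitivity to the assumed timing.**

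| Assumed deviations | Dose on target | Dose varies independently, same distribution |
|---|---|---|
| Uniform ±7 days | 46.7% | 46.7% |
| Triangular | 43.8% | 45.8% |
| Normal, SD 3 days | 43.3% | 45.2% |
| Normal, SD 2 days | 40.1% | 43.0% |
| Normal, SD 1 day | 30.9% | 36.5% |
| Half exactly on target, rest uniform | 23.3% | 35.0% |
| Normal, SD 3, visits 2 days early on average | 20.9% | not run |
| Normal, SD 3, visits 2 days late on average | 68.1% | not run |

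If visit timing tracks dose timing (correlation 0.9, SD 2 days) the share is 29.7%. Extremely tight timing (SD 0.5 day, dose on target) gives 15.9%. A range of about 20–70% covers the plausible cases but is not a bound.

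**5. What that removes.** For a completer with every scheduled test done, the share of on-treatment records lost is the share outside divided by the number of scheduled post-baseline assessments:

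| | At 46.7% | At 20% to 70% |
|---|---|---|
| ECG (1 of 2) | 23.3% | 10% to 35% |
| Hematology (1 of 3) | 15.6% | 6.7% to 23.3% |
| Chemistry (1 of 5) | 9.3% | 4% to 14% |

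**6. Conflict with SAP 6.4.** The week 52 mapping window has 393 − 352 + 1 = 42 days. For an on-target last dose, days 366–393, or 28 of the 42, lie beyond the cut-off.

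**7. The second boundary.** Week 72 is day 505, and 505 − 337 = 168 days = 24 weeks. The post-treatment period therefore closes on the week 72 target day, and a late End of Follow-up visit lies past its end.

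**The case against.** **The exclusion sentence uses another anchor.** It counts from end of treatment, and the protocol calls week 52 the end-of-treatment visit. If that visit is meant, the interval runs 28 days past it and no week 52 value is lost. This reading cannot be ruled out. But the sentence sets the interval for on-treatment events, and the on-treatment period defined just above it ends 28 days after the last dose. On the visit reading, one section would hold two on-treatment limits about 28 days apart. Either way the text needs correcting.

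**By-visit tables may keep the values.** SAP 6.4 works by nominal visit and retains weeks 60 and 72, which a strict exclusion would empty. This is fair: loss from the by-visit tables is a contradiction between two sections, not a settled outcome.

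**A fixed 28-day period is legitimate.** It matches the protocol's own analysis definition and the SAP's exposure formula, and it does not depend on attendance. That stands, and for AEs it is a good reason to leave the period as it is. Treatment period 2 running through week 52 is a conduct period, so on its own it does not show a conflict with the analysis definition.

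**The cut is the same in every arm** and does not touch the primary incidence-rate comparisons. Also true; the issue is completeness of the on-treatment summaries, not bias between arms.

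**Conclusion.** The point holds in a limited form. The cut-off and the week 52 target coincide, no window allowance is made, and with the exclusion limit read as last dose + 28 days, laboratory, ECG and vital-sign values from a compliant but relatively late week 52 visit leave the on-treatment summaries. The size is 46.7% of in-window visits under uniform timing, with a plausible range of about 20–70%; every percentage rests on assumed timing. The clearest consequence is for laboratory PCSVs, which have no other specified summary table, in a trial whose primary endpoint names laboratory change to week 52.

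A reader might infer more than the documents support:

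- *That a narrow band such as 40–47% is established.* It needs symmetric timing with a spread of about two days or more; early, late or tight scheduling moves it well outside.
- *That week 52 radiographs or arthropathies are lost.* The exclusion sentence does not name imaging. Joint space width is summarized at scheduled visits (SAP 4.5.10), and adjudicated arthropathy counts in rates over the observation period (SAP 4.5.1, 5.1.7.1).
- *That AEs are lost.* An AE starting more than 28 days after the last dose is reclassified as post-treatment, and SAP 5.1.8.1 summarizes post-treatment and all-study AEs in the same way as TEAEs.
- *That events at a late week 72 visit belong to no period.* For AEs the post-treatment definition in SAP 5.1.8.1 has no upper limit. The second boundary matters only for the post-treatment PCSV summaries.

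Overall ECG and vital-sign PCSV tables are also unaffected.

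**What to change.** In SAP 5.1.7:

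1. Reconcile the two anchors: say whether the exclusion interval runs from the last dose or from the end of treatment, and define the latter if it is kept.
2. State that laboratory, ECG and vital-sign assessments from the nominal week 52/end-of-treatment visit, or mapped to week 52 under SAP 6.4, count as on-treatment for descriptive and PCSV summaries, whatever the number of days since the last dose. Make clear that for a patient who stops early the end-of-treatment visit takes this role, so that a week 52 visit attended long after stopping is not swept in.
3. Let the nominal End of Follow-up visit count in the post-treatment PCSV summaries.
4. Leave the AE on-treatment period at last dose + 28 days.
5. Record the rule in SAP 1.2.4 as a departure from Protocol 9.5.3.

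A visit-based rule is better than a longer fixed tail. A cap of 42 days, for example, would fail when the week 48 dose is missed: Protocol 5.1 does not allow it to be given late, and week 52 then falls about 56 days after the week 44 dose (365 − 309).

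The cost is a few sentences and one derivation flag. The downside is that some values taken more than 28 days after the last dose are labelled on-treatment, by the same rule in all arms.

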**Table 1: Schedule of Events - Screening through Week 16 Visit**

Study Week	Screening Period	Pre-Randomization Period	Treatment Period				
		Pre-Randomization Phone Call	(Baseline)	4	8	12	16
Study Day (visit window)	Up to 30 days	7 to 10 days	1	29 (±7)	57 (±7)	85 (±7)	113 (±7)
Screening/Baseline:							
Informed Consent	X						
Inclusion/Exclusion 	X	X	X				
Genomics sub-study informed consent 	X						
Medical History	X						
Medication history	X						
Demographics	X						
Height	X						
Electrocardiogram	X						
Bilateral radiograph (knee, hip, shoulder) 	X 						
WOMAC Pain Subscale	X 		X				
MRI 	X						
Randomization			X				
Treatment:							
Discontinue non-study pain meds		X					
SC Study Drug Injection 			X	X	X	X	X
Dispense paracetamol/acetaminophen			X	X	X	X	X

Study Week	Screening Period	Pre-Randomization Period	Treatment Period				
		Pre-Randomization Phone Call	(Baseline)	4	8	12	16
		7 to 10 days	1	29 (±7)	57 (±7)	85 (±7)	113 (±7)
Paracetamol/acetaminophen accountability				X	X	X	X
Dispense NSAID medication							X
Recording of rescue treatment use in diary 			X	X	X	X	X
Concomitant medications	X	X	X	X	X	X	X
Safety:							
Weight	X						X
Vital Signs 	X		X	X	X	X	X
Physical Examination	X						X
Injection site evaluation			X	X	X	X	X
Orthostatic blood pressure 	X		X	X	X	X	X
Joint Pain Questionnaire	X		X	X	X	X	X
Survey of autonomic symptoms	X		X	X	X	X	X
Neurologic examination	Full		Brief	Brief	Brief	Brief	Full
Adverse Events	X	X	X	X	X	X	X
Event-triggered imaging 				X	X	X	X
Pre-op questionnaire (JR) 							
Laboratory Testing:							
Hematology	X						X
Blood Chemistry	X			X	X		X
Erythrocyte sedimentation rate	X						

Study Week	Screening Period	Pre-Randomization Period	Treatment Period				
		Pre-Randomization Phone Call	(Baseline)	4	8	12	16
Study Day (visit window)	Up to 30 days	7 to 10 days	1	29 (±7)	57 (±7)	85 (±7)	113 (±7)
HbA1c	X						
FSH and estradiol 	X						
Pregnancy test (WOCBP)	Serum 		Urine 	Urine 	Urine 	Urine 	Urine 
Urinalysis and Urine Creatinine and Phosphorous	X			X	X		X
PK/Drug Concentration and ADA Samples:							
PK/Drug concentration sample 							X
ADA sample 			X				X
Genomics sub-study sample 			X				

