4.5. Safety Variables

Patient safety will be assessed through the collection of reported adverse events (AEs), clinical laboratory data, vital signs, ECG, Survey of Autonomic Symptoms Questionnaire, neurological exams and physical exams. Unless otherwise noted, the baseline value is defined as the last available value before the first dose of study drug.

Adverse events (AE) and Serious Adverse Events (SAE) will be collected from the time of informed consent signature and then at each visit until the End of Follow-up Clinic Visit. All AEs are to be coded to a “Preferred Term (PT)” and associated primary “System Organ Class SOC” according to the MedDRA[®] (the latest current available version).

An Adverse Event is any untoward medical occurrence in a patient or clinical investigation patient administered a pharmaceutical product and which does not necessarily have to have a causal relationship with this treatment.

A Serious Adverse Event is an adverse event (AE) that is classified as serious according to the criteria specified in the protocol.

Laboratory results, vital signs, or ECG abnormalities are to be recorded as AEs if they are medically relevant: symptomatic, requiring corrective therapy, leading to treatment discontinuation and/or fulfilling a seriousness criterion.

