4.5.1. Primary Safety Variables

The primary safety endpoint in the study is safety monitoring including AE incidence, SAE, incidence, AESI incidence, changes in safety lab analyses, and incidence of anti-fasimumab antibody formation from baseline to week 52 (treatment period 1 and 2) and to week 72 (end of follow-up period).

More specifically, this includes:

- Incidence of adjudicated arthropathy events
- Incidence of destructive arthropathy events
- Incidence of JR (All JRs and AESI JRs) events – including endpoint for all JRs by the telephone survey approximately 52 weeks after the last dose of study drug
- Incidence of peripheral neurosensory AESI events

- Incidence of sympathetic nervous system dysfunction AESI events
- AE incidence, SAE incidence, changes from baseline in safety laboratory analyses, and incidence of anti-fasimumab antibody formation
- Change from baseline in minimum joint space width of the index joint (knee, hip)
- Incidence of confirmed orthostatic hypotension from baseline

The raw incidence rate is defined as the number of events divided by the duration of the observation period and presented as number of events per 100 patient-years.

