5.1.7.1. Primary Safety Endpoints

Incidence rate ratio estimates and 2-sided 95% confidence interval will be computed using Generalized Estimating Equations with a log-linked Poisson model via the PROC GENMOD procedure if there are events in the placebo group. The model will specify the use of a Poisson probability distribution with an offset= log (patient-observation period days) and model terms for treatment-as-received and each randomization strata. The 95% confidence interval for the

estimates of the difference in incidence rates will be computed using the same model. If there is no event in the placebo group, incidence rate ratio will not be calculated and confidence intervals for the incidence rate difference will be computed using Wald method. The incidence rate estimates for each arm, the estimates of the incidence rate ratio and incidence rate difference between fasinumab and placebo will be provided with the corresponding 95% confidence interval.

AE and SAE incidence will be summarized by treatment group based on the SAF-LTS by treatment group and combined fasinumab group.

Continuous variables will be summarized by baseline and change from baseline to each scheduled assessment time with descriptive statistics based on the SAF-LTS by treatment group and combined fasinumab group.

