5.1.8.3. Clinical Laboratory Measurements

Laboratory test results will be summarized by baseline and change from baseline to each scheduled assessment time with descriptive statistics based on the SAF-LTS by treatment group and combined fasinumab group.

Shift tables based on baseline normal/abnormal and other tabular and graphical methods may be used to present the results for laboratory tests of interest.

Listings will be provided with flags indicating the out of laboratory range values.

A Treatment-Emergent Potential Clinically Significant abnormal value (PCSV) is a laboratory value that was normal at Screening and Baseline but became abnormal and met PCSV criteria after treatment with study drug. Definition of PCSV is listed in [Appendix 11.2](#). Treatment Emergent Potentially clinically significant values (PCSVs) will be summarized based on the SAF-LTS by treatment group and combined fasinumab group. Additional exploratory analyses using alternative cut-points may be conducted.

For hs-CRP, plots of means and medians of the observed values and change from baseline over time will presented by treatment group.

For hs-CRP, subgroup analysis will be performed for the following:

- Baseline hs-CRP ([0 – 3], [>3 -10], [>10])
- Adjudicated Arthropathy category 1 (patients without / with AA)
- Adjudicated Arthropathy category 2 (patients without AA, patients with RPOA-1, and patients with non-RPOA-1 AA)
- Destructive Arthropathy category (patients without AA, patients with non-DA AA, patients with DA)

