5.1.8.4. Analysis of Vital Signs

Vital signs (temperature, pulse, blood pressure, orthostatic blood pressure/heart rate, and respiration rate) will be summarized by baseline and change from baseline to each scheduled assessment time with descriptive statistics by treatment group and combined fasinumab for the SAF-LTS.

PCSV summary including orthostatic hypotension will be constructed for on-treatment period, post-treatment period and overall during the LTS study.

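### SAP 5.1.7 excludes laboratory, ECG and vital-sign data after the on-treatment interval without limiting the rule to on-treatment summaries, which contradicts planned follow-up summaries; separately, the injection table stops at 12 of 13 doses

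*SAP*

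**What the plan says.** SAP 5.1.7 divides observation into pre-treatment, on-treatment and post-treatment segments. The on-treatment segment ends 28 days after the last dose. It then introduces a detection interval: "The time interval to detect any on-treatment event or abnormality is between the first dose of double-blind study drug injection and the end of treatment", to which it adds 28 days. The next sentence is the rule at issue: "Data collected outside this interval will be excluded from the estimation of descriptive statistics and identification of abnormalities for laboratory evaluations, ECGs and vital signs". A further sentence says that post-baseline data within the interval, scheduled or not, enter the PCSV analysis.

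Other sections plan outputs that need data from after that interval:

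- SAP 4.5.1 lists change in safety laboratory values among the primary safety variables, observed "from baseline to week 52 (treatment period 1 and 2) and to week 72 (end of follow-up period").
- SAP 5.1.7.1: "Continuous variables will be summarized by baseline and change from baseline to each scheduled assessment time with descriptive statistics".
- SAP 5.1.8.3: "Laboratory test results will be summarized by baseline and change from baseline to each scheduled assessment time with descriptive statistics". SAP 5.1.8.4 and 5.1.8.5 say the same for vital signs and ECG.
- SAP 5.1.8.4: "PCSV summary including orthostatic hypotension will be constructed for on-treatment period, post-treatment period and overall during the LTS study". SAP 5.1.8.5 plans the same three periods for ECG.

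On dosing, Protocol 5.1 gives every patient an injection every 4 weeks from day 1 to week 48. SAP 5.1.6.1 tabulates patients by number of injections, from 1 to 12.

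**The concern.** Two careful programmers could produce different tables from this SAP. One who applies 5.1.7 literally would leave follow-up laboratory, ECG and vital-sign values out of the by-visit statistics and would have no data for the post-treatment PCSV tables. One who applies 5.1.7.1 and 5.1.8.3 to 5.1.8.5 would include them. Nothing says which section governs.

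Laboratory values are the most exposed. For vital signs and ECG the SAP names post-treatment and overall PCSV summaries, which signal that follow-up data are wanted. SAP 5.1.8.3 names no such period for laboratory data, although laboratory change to week 72 is a primary safety variable in a study whose primary objective is safety.

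The injection table is a smaller matter. A patient who receives every planned dose has no category.

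**Working it through.** **Inputs.** Assessment schedule: Protocol Tables 1, 2 and 4. Last dose: week 48 (Protocol 3.1 and 5.1). Visit target days: SAP 6.4. Visit tolerance: ±7 days.

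**Step 1: reproduce the SAP's target days.** Study day = 7 × week + 1. Week 48: 7 × 48 + 1 = 337. Week 52: 365. Week 60: 421. Week 72: 505. All match SAP 6.4.

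**Step 2: find the end of the interval for an on-target, fully dosed patient.**

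- Last dose plus 28 days: 337 + 28 = 365.
- If end of treatment were taken as the week 52 visit: 365 + 28 = 393.

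Week 60 (day 421) and week 72 (day 505) lie beyond both.

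**Step 3: allow for the visit tolerance.**

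- Last-dose reading: the latest cut-off is 337 + 7 + 28 = 372. The earliest week 60 visit is then day 421 − 7 = 414, which is 42 days later.
- Visit reading: the latest cut-off is 365 + 7 + 28 = 400. The earliest week 60 visit, counted from an early last dose, is 337 − 7 + 84 − 7 = 407, which is 7 days later.

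Weeks 60 and 72 are therefore outside in every case.

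**Step 4: count scheduled post-baseline assessments, main-study schedule.**

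| Assessment | Weeks scheduled | Outside | Share |
|---|---|---|---|
| Chemistry, urinalysis | 4, 8, 16, 32, 52, 72 | 72 | 1 of 6 |
| Haematology | 16, 32, 52, 72 | 72 | 1 of 4 |
| ECG | 28, 52, 60, 72 | 60, 72 | 2 of 4 |
| Vital signs, orthostatic blood pressure | 4 to 48 every 4 weeks (12 visits), 52, 60, 72 | 60, 72 | 2 of 15 |

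No chemistry, haematology or urinalysis is scheduled at week 60, so the week 60 conflict concerns ECG and vital signs only.

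**Step 5: week 52.** The visit may fall on days 358 to 372. After an on-target last dose, the last-dose cut-off is day 365, so visits on days 366 to 372 are within the protocol window but outside the interval. These are calendar days, not an estimate of data lost.

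**Step 6: injections.** 48/4 + 1 = 13 (weeks 0, 4, …, 48). The count is the same in all arms, because patients on the 8-weekly regimen receive placebo at alternate visits. The listed maximum of 12 is not reproduced. Omitting day 1 or stopping at week 44 would each give 12, but both contradict the schedule. The SAP's other lists agree with 13: the exposure thresholds in 5.1.6.2 number 13 and fall on the 13 dosing days (1, 29, …, 337), and the sub-study list of 1 to 4 in 5.2.6.1 matches weeks 0, 4, 8 and 12.

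**The case against.** The best defence is that the text supplies the scope. The excluded data are those outside an interval that the preceding sentence introduces as the on-treatment one. The section has just separated three segments, and 5.1.8.4 and 5.1.8.5 then name on-treatment, post-treatment and overall tables. On that view a single phrase is missing. This stands as evidence of intent. It does not settle the matter, because the exclusion is worded generally, does not defer to the later sections, and for laboratory data has no named post-treatment table to correct it.

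Two further defence points also stand. The affected outputs are descriptive tables. The window table in SAP 6.4 is generic: it includes weeks 1, 2 and 60, when no chemistry or haematology is scheduled, so its week 60 and 72 rows are weak evidence and the point does not rest on them.

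On injections, little information is lost. With on-schedule dosing, 12 consecutive doses give 309 − 1 + 28 = 336 days of exposure and 13 give 337 − 1 + 28 = 364. The row for at least 337 days in 5.1.6.2 therefore picks out patients dosed through week 48, apart from any who skipped an earlier dose.

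A reader might infer more than the documents support:

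- *That baselines are lost.* SAP 4.5 says "the baseline value is defined as the last available value before the first dose of study drug", and the protocol's "Schedule of Events - Screening through Week 16 Visit" table places pre-dose chemistry, haematology, urinalysis and ECG at screening only, before the interval opens. But 5.1.7 itself goes on to speak of post-baseline data within the interval, 4.5.4 and 4.5.6 define change as post-baseline minus baseline, and 6.5 says how baselines are determined. Dropping baselines is not a credible reading.
- *That 5.1.7 conflicts with the rule in 6.4 admitting scheduled and unscheduled values.* SAP 5.1.7 states the same rule. The 6.4 sentence concerns the type of assessment and sets no time period.
- *That the interval is undefined because end of treatment is not explained.* The same section ends the on-treatment period 28 days after the last dose, as does Protocol 9.5.3 (4 weeks). This is a wording mismatch, and it does not change the week 60 and 72 result.

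**Conclusion.** The point holds as an internal contradiction that should be corrected. As written, 5.1.7 drops week 72 for chemistry, urinalysis and haematology (1 of 6, 1 of 6 and 1 of 4 post-baseline assessments) and weeks 60 and 72 for ECG and vital signs (2 of 4 and 2 of 15). Other sections of the SAP plan to summarise these data.

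The counts assume a fully dosed patient on the main-study schedule. Patients who stop drug early are asked to attend the remaining visits (Protocol 5.3.2), so more of their values could fall outside; the documents do not allow that share to be estimated. The intended meaning was probably on-treatment only, so this is an ambiguity to close and not evidence that follow-up data will in fact be discarded.

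Adverse-event, arthropathy and joint-replacement rates are unaffected. Nor do the documents require post-treatment laboratory PCSV tables: SAP 5.1.8.3 and Protocol 9.5.3.2 name no period for them.

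The missing 13-injection category is a certain but minor error that affects one display. The compliance percentage is unaffected.

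**What to change.** In SAP 5.1.7:

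1. Limit the exclusion explicitly to on-treatment summaries.
2. State that by-visit descriptive statistics use all post-baseline data through week 72, and that post-treatment and overall summaries use follow-up data.
3. Replace the end-of-treatment wording with the section's own definition, last dose plus 28 days, and state that in-window week 52 visits stay in the week 52 by-visit summary even when they fall after that cut-off.

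In SAP 5.1.6.1, add a category for 13 injections.

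The cost is a few sentences of SAP text, minor programming and one table category. Data collection and the on-treatment definition do not change.
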